3.3 Number of Patients and Centers

Total enrollment of approximately 180 patients is planned for the study. Approximately 75 patients will be enrolled in the dose escalation portion of the study for ALRN-6924 as single agent therapy, and approximately 15-25 additional patients per expansion cohort will be enrolled in up to 5 expansion cohorts in the expansion part of the study. The expansion cohort of patients with MDM2 amplified or MDM2/CDK4 co-amplified solid tumors is planned to include approximately 10 patients with MDM2/CDK4 co-amplification. In the event that the distribution of patients with MDM2 amplified versus MDM2/CDK4 co-amplified tumors becomes imbalanced, the sponsor may temporarily suspend enrollment to one group to facilitate enrollment in the other.

Approximately 15 to 25 clinical sites are planned.

3.4 Duration of Study

The expected accrual phase is approximately 54 months. The expected follow-up phase is approximately 8 months after the last patient is enrolled, for a total study duration of approximately 62 months.

4 PATIENT POPULATION

The study will enroll adult or adolescent patients with advanced solid tumors or lymphomas who are expected to have WT TP53 and are refractory to or intolerant of standard therapy, or for whom no standard therapy exists. The distinct inclusion/exclusion criteria for each cohort are presented in the remainder of this section.

4.1 Inclusion Criteria – Phase 1 dose escalation (ALRN-6924 administered as single agent therapy)

Patients must meet all of the following criteria to be considered for participation in this study:

1. Male or female patients age 18 years and older, inclusive, at the time of informed consent
2. Histologically- or cytologically-confirmed solid tumors that are metastatic or unresectable or lymphomas. Standard measures do not exist or are no longer effective for these patients.
3. WT TP53 status for relapsing or treatment-refractory solid neoplasms and lymphomas is mandatory for patients enrolling at Dose Level 4 and higher in Stage 1 of the DEP as well as for all patients enrolled in Stage 2 of the DEP or in the EXP. In EXP, beginning with Amendment 6, TP53 status still must be determined by the central laboratory, but confirmation of WT TP53 status is not required for enrollment or initiation of study treatment, if the Investigator deems it clinically unacceptable to delay treatment.
4. At least one target lesion that is measurable by RECIST 1.1 in patients with solid tumors or by IWG (2014) criteria in patients with lymphoma.
5. ECOG performance status 0-1
6. Predicted life expectancy of ≥ 3 months
7. Adequate hematologic bone marrow function, measured within 7 days prior to the first dose of ALRN-6924, defined as:
 - ANC $\geq 1.5 \times 10^9/L$
 - Hemoglobin $\geq 9.0 \text{ g/dL}$
 - Platelets $\geq 100 \times 10^9/L$
8. Adequate hepatic function, measured within 7 days prior to the first dose of ALRN-6924, defined as:
 - In the absence of disease involvement in the liver: bilirubin ≤ 1.5 times institutional ULN as well as AST and ALT ≤ 2.5 times ULN
 - In the presence of disease involvement in the liver: bilirubin ≤ 2 times ULN as well as AST and ALT ≤ 5 times ULN
9. Adequate renal function, measured within 7 days prior to the first dose of ALRN-6924, defined as:
 - Urinalysis with no evidence of +2 or higher proteinuria

- Serum creatinine \leq 1.5 times institutional ULN or calculated creatinine clearance \geq 50 mL/min (Cockcroft-Gault formula)

10. Acceptable coagulation profile, measured within 7 days prior to the first dose of ALRN-6924, defined as:

- PT or INR \leq 1.5 times ULN
- aPTT \leq 1.5 times ULN

11. Prior anti-cancer therapies must wash-out such that they can neither cause drug-drug interaction with ALRN-6924 nor interfere with the anti-cancer evaluation of ALRN-6924. Therefore, the wash-out has to meet all the following criteria:

- patients must have recovered from the previous therapy to Grade 1 or baseline of significant toxicities, excluding alopecia, and
- 5 half-lives or 4 weeks (whichever is shorter) must have expired, unless the prior anti-cancer therapy and ALRN-6924 do not interfere with each other's metabolism, and
- 5 half-lives or 4 weeks (whichever is shorter) must have expired, unless the patient unequivocally progressed during the prior anti-cancer therapy

Palliative radiotherapy for bone lesions \leq 2 weeks prior to the first dose of ALRN-6924 is acceptable if acute toxicity has resolved

12. Negative serum or urine pregnancy test within 2 days prior to the first dose of ALRN-6924 for women of child-bearing potential, defined as a sexually mature woman who has not undergone a hysterectomy or who has not been naturally post-menopausal for \geq 24 consecutive months (i.e., who has had menses any time in the preceding 24 consecutive months)

13. All patients (males and females) of child-bearing potential must agree to use an effective method of birth control (i.e., latex condom, diaphragm, cervical cap, IUD, birth control pill, etc.) beginning two weeks before the first dose of ALRN-6924 and for 30 days after the last dose of ALRN-6924

14. Ability to understand and willingness to sign a written informed consent form

15. Patients with prostate cancer must continue androgen deprivation therapy, unless such therapy was discontinued 6 months prior to first dose of ALRN-6924

4.2 Exclusion Criteria – Phase 1 dose escalation (ALRN-6924 administered as single agent therapy)

Patients who meet any of the following criteria at screening or Day -1 will be excluded:

1. Previous treatment with investigational agents that inhibit MDM2 or MDMX activity with the following exception:
Patients previously treated with an MDM2-inhibitor are eligible provided that a biopsy taken after completion of the last treatment with an MDM2-inhibitor is confirmed as WT TP53 prior to enrollment.
2. Known hypersensitivity to any study drug component

3. Known and untreated brain metastases. Patients with brain metastases that have been treated and demonstrated to be clinically stable for ≥ 30 days may be enrolled. Patients with primary CNS malignancies are excluded.
4. Current, clinically significant coagulopathy or platelet disorder, as determined by the Investigator
5. History of pulmonary embolism within 6 months prior to the first dose of ALRN-6924 or untreated DVT
6. Required concurrent use of anti-coagulants or anti-platelet medication, with the exception of aspirin doses ≤ 81 mg/day, low-dose SC heparin or SC low-molecular-weight heparin for DVT prophylaxis, or heparin flushes to maintain IV catheter patency.
7. Patients with pre-existing history of or known cardiovascular risk:
 - History of acute coronary syndromes within 6 months prior to the first dose of ALRN-6924 (including myocardial infarction, unstable angina, coronary artery bypass graft, angioplasty, or stenting).
 - Uncontrolled hypertension
 - Pre-existing cardiac failure (New York Heart Association class III-IV)
 - Atrial fibrillation on anti-coagulants.
 - Clinically significant uncontrolled arrhythmias
 - Severe valvulopathy.
 - Corrected QTc interval on screening ECG ≥ 450 msec for males and ≥ 470 msec for females (QTc > 480 msec for any patient with a bundle branch block).
8. Clinically significant gastrointestinal bleeding within 6 months prior to the first dose of ALRN-6924.
9. Clinically significant third-space fluid accumulation (e.g., ascites requiring tapping despite the use of diuretics, or pleural effusion that requires tapping or is associated with shortness of breath).
10. Pregnant or lactating females.
11. Evidence of serious and/or unstable pre-existing medical, psychiatric or other condition (including laboratory abnormalities) that could interfere with patient safety or provision of informed consent to participate in this study.
12. Active uncontrolled infection, including HIV/AIDS or hepatitis B or C in the absence of hepatocellular carcinoma. Patients with primary liver cancer that have positive hepatitis serology but are not demonstrating active viral hepatitis may be considered for enrollment if they meet all other inclusion and no other exclusion criteria.
13. Starting at Dose Level 4 and higher of Stage 1 of the DEP, as well as for all patients enrolling in Stage 2 of the DEP or in the EXP, patients with an HPV-positive malignancy.

14. Known history of another primary malignancy that has not been in remission for ≥ 2 years. Non-melanoma skin cancer and cervical carcinomas *in situ* or squamous intraepithelial lesions (e.g., CIN or PIN) are allowed.
15. Any psychological, sociological, or geographical condition that could potentially interfere with compliance with the study protocol and follow-up schedule.
16. The required use of any concomitant medications that are predominantly cleared by hepatobiliary transporters, OATP members OATP1B1 and OATP1B3, on the day of the ALRN-6924 infusion or within 48 hours after an ALRN-6924 infusion.
17. Hereditary angioedema of any severity or history of severe or life-threatening angioedema, due to any cause

4.3 Inclusion Criteria – Phase 2a dose expansions in PTCL (ALRN-6924 administered as single agent therapy)

1. Male or female patients age 18 years and older, inclusive, at the time of informed consent
2. A histologically confirmed diagnosis of PTCL based on pathology review at the local institution, using the most recent edition of the WHO Classification of Tumors of Haematopoietic and Lymphoid Tissues as guidance.

The pathology sample must be considered to be adequate, meaning that there must be enough well-preserved, formalin-fixed biopsy material for the pathologist to be able to perform a morphological and immunohistochemical examination so as to in confidence be able to state an unequivocal diagnosis of PTCL. Final diagnoses containing caveats such as “suspicious of” or “presumably” are considered inadequate for a patient to be enrolled in the trial. In addition, a pathology sample must be available for a central pathology read.

3. Patients must have relapsed or refractory disease after at least one but not more than 7 prior systemic anticancer regimens.
4. WT TP53 status of t-cell lymphoma cells. Beginning with Amendment 6, TP53 status still must be determined by the central laboratory, but confirmation of WT TP53 status is not required for enrollment or initiation of study treatment, if the Investigator deems it clinically unacceptable to delay treatment.
5. At least one target lesion that is measurable by Revised International Working Group Response Criteria for lymphoma patients (IWG 2014 - See [Appendix L](#)). Patients with PTCL subtypes that are assessed by alternative criteria must have measurable disease in accordance with those criteria and be approved by the Medical Monitor.
6. Eastern Cooperative Oncology Group (ECOG) performance status 0-1 (See [Appendix A](#))
7. Predicted life expectancy of ≥ 3 months
8. Adequate hematological bone marrow function, measured within 7 days prior to the first dose of ALRN-6924, defined as:
 - Absolute neutrophil count (ANC) $\geq 1.0 \times 10^9/L$

- Platelets $\geq 50 \times 10^9/L$ (platelets $< 50 \times 10^9/L$ are acceptable if partly caused by autoimmune destruction and/or splenomegaly and/or hepatic disease infiltration)

9. Adequate hepatic function, measured within 7 days prior to the first dose of ALRN-6924, defined as:

- Total bilirubin $\leq 1.5 \times$ upper normal limit, or $\leq 3 \times$ upper normal limit if documented hepatic infiltration with lymphoma
- Aspartate aminotransferase (AST) and alanine aminotransferase (ALT) $\leq 2.5 \times$ upper normal limit ($\leq 5 \times$ upper normal limit if documented hepatic infiltration with lymphoma)

10. Adequate renal function, measured within 7 days prior to the first dose of ALRN-6924, defined as serum creatinine ≤ 1.5 times institutional ULN, or calculated creatinine clearance ≥ 50 mL/min (Cockcroft-Gault formula)

11. Acceptable coagulation profile, measured within 7 days prior to the first dose of ALRN-6924, defined as:

- Prothrombin time (PT) or international normalized ratio (INR) ≤ 1.5 times ULN
- Activated partial thromboplastin time (aPTT) ≤ 1.5 times ULN

12. Prior anti-cancer therapies must wash-out such that they can neither cause drug-drug interaction with ALRN-6924 nor interfere with the anti-cancer evaluation of ALRN-6924. Therefore, the wash-out has to meet all the following criteria:

- patients must have recovered from the previous therapy to \leq Grade 1 or baseline of significant toxicities, excluding alopecia, and
- 5 half-lives or 4 weeks (whichever is shorter) must have expired, unless the prior anti-cancer therapy and ALRN-6924 do not interfere with each other's metabolism, and
- 5 half-lives or 4 weeks (whichever is shorter) must have expired, unless the patient unequivocally progressed during the prior anti-cancer therapy

Palliative radiotherapy for bone lesions ≤ 2 weeks prior to the first dose of ALRN-6924 is acceptable if acute toxicity has resolved

13. Negative serum or urine pregnancy test within 2 days prior to the first dose of ALRN-6924 for women of child-bearing potential, defined as a sexually mature woman who has not undergone a hysterectomy or who has not been naturally post-menopausal for ≥ 24 consecutive months (i.e., who has had menses any time in the preceding 24 consecutive months)

14. All patients (males and females) of child-bearing potential must agree to use an effective method of birth control (i.e., latex condom, diaphragm, cervical cap, intra-uterine device [IUD], birth control pill, etc.) beginning two weeks prior to the first dose of ALRN-6924 and for 30 days after the last dose of ALRN-6924

15. Ability to understand and willingness to sign a written informed consent form

4.4 Exclusion Criteria – Phase 2a dose expansions in PTCL (ALRN-6924 administered as single agent therapy)

1. Previous treatment with investigational agents that inhibit MDM2 or MDMX activity
2. Relapse within 75 days of autologous bone marrow transplant.
3. Prior allogeneic stem cell transplantation, unless immunosuppressants are no longer required and there is no active graft versus host disease.
4. Known central nervous system (CNS) lymphoma [computed tomography (CT) or magnetic resonance imaging (MRI) scans are required only if brain metastasis is suspected clinically]
5. Known hypersensitivity to any study drug component
6. Current, clinically significant coagulopathy or platelet disorder, as determined by the Investigator
7. Required concurrent use of anti-coagulants or anti-platelet medication, with the exception of aspirin doses \leq 81 mg/day, low-dose subcutaneous (SC) heparin or SC low-molecular-weight heparin for DVT prophylaxis, or heparin flushes to maintain IV catheter patency.
8. Patients with pre-existing history of or known cardiovascular risk:
 - History of acute coronary syndromes within 6 months prior to the first dose of ALRN-6924 (including myocardial infarction, unstable angina, coronary artery bypass graft, angioplasty, or stenting)
 - Uncontrolled hypertension
 - Pre-existing cardiac failure (New York Heart Association Class III-IV)
 - Atrial fibrillation on anti-coagulants
 - Clinically significant uncontrolled arrhythmias
 - Severe valvulopathy
 - Corrected QT (QTc) interval on screening electrocardiogram (ECG) \geq 450 msec for males and \geq 470 msec for females (QTc $>$ 480 msec for any patient with a bundle branch block)
9. Clinically significant gastrointestinal bleeding within 6 months prior to the first dose of ALRN-6924
10. Clinically significant third-space fluid accumulation (e.g., ascites requiring tapping despite the use of diuretics; or pleural effusion that requires tapping or is associated with shortness of breath)
11. Pregnant or lactating females
12. Evidence of serious and/or unstable pre-existing medical, psychiatric, or other condition (including laboratory abnormalities) that could interfere with patient safety or provision of informed consent to participate in this study
13. Active uncontrolled infection, including HIV/AIDS or Hepatitis B or C

14. Known history of another primary malignancy that has not been in remission for ≥ 1 year. Non-melanoma skin cancer and cervical carcinomas in situ or squamous intraepithelial lesions (e.g., cervical intraepithelial neoplasia [CIN] or prostatic intraepithelial/intraductal neoplasia [PIN]) are allowed.
15. Any psychological, sociological, or geographical condition that could potentially interfere with compliance with the study protocol and follow-up schedule
16. The required use of any concomitant medications that are predominantly cleared by hepatobiliary transporters, organic anion transporter polypeptide [OATP] members OATP1B1 and OATP1B3, on the day of the ALRN-6924 infusion or within 48 hours after an ALRN-6924 infusion (see [Appendix B](#))
17. Hereditary angioedema of any severity or history of severe or life-threatening angioedema, due to any cause.

4.5 Inclusion Criteria - Phase 2a Dose Expansion in MDM2 Amplified or MDM2/CDK4 Co-amplified Solid Tumors (ALRN-6924 plus palbociclib)

1. Histologically-confirmed solid tumor malignancy:
 - a. for which there is no curative treatment and that is relapsed or refractory following at least one prior line of medical therapy; and
 - b. that is either MDM2 amplified or MDM2/CDK4 co-amplified, based on local or central laboratory testing by NGS, FISH, or CGH. Tissue must be available for analysis at a central laboratory, even if enrolling based on alternative (e.g., local or commercial) test results. Alternative laboratory results require approval by the Medical Monitor prior to enrollment. Specimens must have been obtained after any previous exposure to palbociclib or any other CDK4/6 inhibitor.
2. At least one target lesion that is measurable by RECIST 1.1 or RANO or other appropriate response criteria
3. Males and females aged 12 years and older
4. ECOG performance status of 0 to 1
5. Adequate hematopoiesis, defined as:
 - a. Absolute neutrophil count $\geq 1.5 \times 10^9/L$
 - b. Hemoglobin $\geq 9.0 \text{ g/dL}$ (without transfusions in the past 2 weeks)
 - c. Platelets $\geq 100 \times 10^9/L$
 - d. Absolute lymphocyte count $\geq 0.5 \times 10^9/L$
6. Adequate hepatic function, defined as:
 - a. In the absence of disease involvement of the liver: bilirubin ≤ 1.5 times institutional ULN, and AST and ALT ≤ 2.5 times ULN

- b. In the presence of disease involvement of the liver: bilirubin \leq 2 times institutional ULN and AST and ALT \leq 5 times ULN
- 7. Adequate renal function, defined as serum creatinine \leq 1.5 times institutional ULN, or calculated creatinine clearance \geq 50 mL/min (Cockcroft Gault formula)
- 8. Five half-lives or 4 weeks, whichever is shorter, must have elapsed since any prior anticancer agent was administered, unless the patient unequivocally progressed during that therapy and the agent would not be expected to interfere with ALRN-6924 or palbociclib metabolism or impede clinical assessments
- 9. Recovery from the acute toxic effects of all prior therapies to \leq Grade 1 or baseline, excluding alopecia
- 10. Provision of informed consent and, where applicable, pediatric assent
- 11. Agreement to use acceptable methods of pregnancy prevention, if of child-bearing potential

4.6 Exclusion Criteria - Phase 2a Dose Expansion in MDM2 Amplified or MDM2/CDK4 Co-amplified Solid Tumors (ALRN-6924 plus palbociclib)

- 1. Tumors with known mutations or deletions in TP53 or Rb
- 2. Known hypersensitivity to any component of study medication
- 3. Symptomatic or untreated CNS metastases
- 4. Pulmonary embolism within the past 6 months or DVT that has not been fully treated.
- 5. Clinically significant cardiovascular risk factors, including:
 - myocardial infarction, unstable angina, coronary artery bypass grafting, stenting, angioplasty, or acute coronary syndrome in the past 6 months
 - New York Heart Association Class III or IV heart failure
 - clinically significant uncontrolled arrhythmia
 - corrected QT (QTc) interval \geq 450 msec for males and \geq 470 msec for females (QTc $>$ 480 msec for any patient with a bundle branch block)
- 6. Uncontrolled hypertension
- 7. Active, uncontrolled infection, including HIV, hepatitis B, or hepatitis C
- 8. HPV-positive malignancy.
- 9. Ascites requiring paracentesis or pleural effusion requiring pleurocentesis or causing dyspnea
- 10. Hereditary angioedema of any severity or history of clinically significant angioedema, due to any cause
- 11. Major surgery within 3 weeks prior to the first dose of ARLN-6924
- 12. History of another malignancy within the past year, excluding nonmelanoma skin cancers, carcinomas in situ, or other malignancies with \geq 95% 5-year survival

13. Pregnant or lactating females
14. Required use of medications that are primarily cleared by hepatobiliary transporters, including organic anion transporters, OATP1B1 and OATP1B3, and bile salt export pump (BSEP), unless administration is not required on the day of or within 48 hours following ALRN-6924 administration
15. Required use of medications that are strong inhibitors or moderate to strong inducers of CYP3A
16. Administration of any investigational agent, regardless of indication, within the 2 weeks prior to enrollment, unless a minimum of 5 half-lives have elapsed
17. Any medical, psychological, or social condition that would interfere with patient safety or the conduct of the study

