Adverse events considered for dose reduction should not include events assessed by the Investigator as exclusively related to underlying disease or other medical condition or concomitant treatment. A patient who experiences an AE considered related to ALRN-6924 that does not meet the requirement for discontinuation may continue on study if the patient is receiving clinical benefit and/or the Investigator feels continued participation is in the best interest of the patient. In such cases, at the Investigator's discretion and in agreement with Sponsor's Medical Monitor, the dose for a patient may be reduced as described above.

A patient who experiences a DLT must continue treatment at a reduced dose level, or discontinue ALRN-6924 treatment (if Grade 4 related AE), as described above at the discretion of the Investigator and in agreement with Sponsor's Medical Monitor until disease progression or unacceptable toxicity. Once the dose has been reduced for a patient, it may not be re-escalated.

Dose Modifications – Phase 2a dose expansions in PTCL (ALRN-6924 administered as single agent therapy)

In the event a non-hematologic Grade 4 AE considered related to ALRN-6924 is observed, the patient must be discontinued from the study. Exceptions include emesis, diarrhea or electrolyte abnormalities that resolve within 2 days on optimum treatment. For these exceptions, treatment may be delayed for up to 2 weeks to allow resolution of the toxicity (i.e., return to Grade ≤ 1 or baseline), followed by re-treatment at a reduced dose. Relevant labs should be repeated as medically indicated.

In the event a non-hematologic Grade 3 AE considered related to ALRN-6924 is observed (exceptions are Grade 3 fatigue, nausea, emesis, diarrhea or clinically insignificant electrolyte abnormalities that resolve within 2 days on optimum treatment), treatment may be delayed for up to 2 weeks to allow resolution of the toxicity, followed by re-treatment at a reduced dose. Relevant labs should be repeated as medically indicated.

For hematologic toxicities, patients must discontinue treatment with ALRN-6924 if

- Neutrophil counts $< 0.5 \times 10^9/L$ for > 5 days, or
- Platelet counts $< 10 \times 10^9/L$, or
- Hemoglobin $< 6 \text{ g/dL}$ (despite RBC transfusion or Erythropoiesis-Stimulating Agent (ESA) administration)

Patients interrupt treatment if

- Neutrophil counts $< 0.5 \times 10^9/L$ for ≤ 5 days, or
- Platelet counts $< 25 \times 10^9/L$ and $> 10 \times 10^9/L$, or

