Adverse events considered for dose reduction should not include the events assessed by the Investigator as exclusively related to underlying disease or other medical condition or concomitant treatment. A patient who experiences an AE considered related to ALRN-6924 that does not meet the requirement for discontinuation may continue on study if the patient is receiving clinical benefit and/or the Investigator feels continued participation is in the best interest of the patient. In such cases, at the Investigator's discretion and in agreement with Sponsor's Medical Monitor, the dose for a patient may be reduced as described above.

A patient who experiences a DLT must continue treatment at a reduced dose level, or discontinue ALRN-6924 treatment (if Grade 4 related AE), as described above at the discretion of the Investigator and in agreement with Sponsor's Medical Monitor until disease progression or unacceptable toxicity. Once the dose has been reduced for a patient, it may not be re-escalated.

5.8.2 Dose Modifications – Phase 2a dose expansions in PTCL (ALRN-6924 administered as single agent therapy)

In the event a non-hematologic Grade 4 AE considered related to ALRN-6924 is observed, the patient must be discontinued from the study. Exceptions include emesis, diarrhea or electrolyte abnormalities that resolve within 2 days on optimum treatment. For these exceptions, treatment may be delayed for up to 2 weeks to allow resolution of the toxicity (i.e., return to Grade ≤ 1 or baseline), followed by re-treatment at a reduced dose. Relevant labs should be repeated as medically indicated.

In the event a non-hematologic Grade 3 AE considered related to ALRN-6924 is observed (exceptions are Grade 3 fatigue, nausea, emesis, diarrhea or clinically insignificant electrolyte abnormalities that resolve within 2 days on optimum treatment), treatment may be delayed for up to 2 weeks to allow resolution of the toxicity, followed by re-treatment at a reduced dose. Relevant labs should be repeated as medically indicated.

For hematologic toxicities, patients must discontinue treatment with ALRN-6924 if

- Neutrophil counts $< 0.5 \times 10^9/L$ for > 5 days, or
- Platelet counts $< 10 \times 10^9/L$, or
- Hemoglobin $< 6\text{g/dL}$ (despite RBC transfusion or Erythropoiesis-Stimulating Agent (ESA) administration)

Patients must interrupt treatment if

- Neutrophil counts $< 0.5 \times 10^9/L$ for ≤ 5 days, or

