- Platelet counts $< 25 \times 10^9/L$ and $> 10 \times 10^9/L$, or
- Hemoglobin $< 8\text{ g/dL}$ and $> 6\text{ g/dL}$

After resolution of hematologic toxicity (i.e., return to Grade ≤ 1 or baseline), patients may continue at a reduced dose. Relevant labs should be repeated as medically indicated.

Following related Grade 3 and Grade 4 AEs (as permitted), the dose for re-treatment will be reduced by 25% intervals (e.g., if the dose is 3.1 mg/kg, the dose will be reduced sequentially to 2.3 mg/kg and 1.7 mg/kg). Two dose reductions are permitted, a third dose reduction will require evidence of clinical benefit and approval by the Medical Monitor.

5.8.3 Dose Modifications – Phase 2a Dose Expansion in MDM2 Amplified or MDM2/CDK4 Co-amplified Solid Tumors (ALRN-6924 plus palbociclib)

Dose modifications of ALRN-6924 will be as described in Section 5.8.1. Dose modifications of palbociclib should be made in accordance with the current approved US prescribing information.

In the event that palbociclib administration must be discontinued, the patient may continue to receive ALRN-6924 as a study participant until one of the criteria for treatment discontinuation has been met. However, if discontinuation of ALRN-6924 is required, patients will be considered to have discontinued study treatment. Those patients may continue to receive palbociclib treatment at the Investigator's discretion.

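### PTCL entry criterion 8 can admit a patient whose platelet count or hemoglobin already lies in the range where section 5.8.2 stops treatment

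*Protocol*

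**What the plan says.** Protocol section 4.3, criterion 8, and its synopsis counterpart define adequate marrow function for PTCL by two values taken in the week before the first dose: ANC at least 1.0 and platelets at least 50 (both x10^9/L). Platelets under 50 "are acceptable if partly caused by autoimmune destruction and/or splenomegaly and/or hepatic disease infiltration". No lower limit is attached to that exception, and hemoglobin is not mentioned. The other two sets of criteria (4.1 for Phase 1, 4.5 for the palbociclib combination) require hemoglobin of at least 9.0 g/dL and platelets of at least 100.

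Section 5.8.2 governs dosing in the same PTCL patients. Its discontinuation list opens "For hematologic toxicities, patients must discontinue treatment with ALRN-6924 if" and its hold list opens "Patients must interrupt treatment if" (in the synopsis, "Patients interrupt treatment if"). Both lists consist of absolute counts. The neighbouring non-hematologic rules are tied to cause, for example "In the event a non-hematologic Grade 3 AE considered related to ALRN-6924 is observed"; the hematologic lists carry no such phrase. Baseline appears once, in the resumption rule: when the toxicity has come back to Grade 1 or better, or to baseline, "patients may continue at a reduced dose". On the size of reductions the section adds: "Following related Grade 3 and Grade 4 AEs (as permitted), the dose for re-treatment will be reduced by 25% intervals".

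The schedules in Appendices C, E and G draw hematology before dosing on Day 1, so the cut-offs can be checked before any drug is given.

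**The concern.** Entry limits and stopping limits normally leave a gap between them, so that a stop signals a change on treatment. Here the eligible range contains the stop range for two of the three blood counts. Faced with a patient who enters with platelets of 20 and still has 20 on Day 1, one site could hold the drug because the count is under 25. Another could treat because nothing has worsened. On the first reading the patient could resume only at a reduced dose although the count never moved, and an expansion patient who misses a Cycle 1 dose may be replaced under section 4.8.

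The drug's nonclinical profile makes this more than a matter of drafting. Section 1.4.2 gives marrow suppression, especially of the platelet lineage, as the dose-limiting toxicity in both animal species. Patients entering with very low counts are the ones for whom the stopping rule most needs to be unambiguous.

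**Working it through.** The plan states no figure to reproduce. The check sets the entry limits against the triggers.

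Inputs: entry limits from 4.3 criterion 8; triggers from 5.8.2. Platelets and ANC are x10^9/L, hemoglobin is g/dL.

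| Count | Entry limit | Interrupt | Discontinue | Eligible values inside a trigger |
|---|---|---|---|---|
| Platelets, base rule | at least 50 | >10 to <25 | <10 | none |
| Platelets, exception | <50, no floor | >10 to <25 | <10 | >10 to <25 (interrupt); <10 (discontinue) |
| Hemoglobin | none | >6 to <8 | <6 despite transfusion or ESA | >6 to <8 (interrupt); <6 only if that condition is met |
| ANC | at least 1.0 | <0.5 for up to 5 days | <0.5 for more than 5 days | none |

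Size of the platelet overlap on the number line: the exception spans 0 to 50. The interrupt band is 25 − 10 = 15 units and the discontinue band is 10 units, so 15 + 10 = 25 of 50, or 50%, lies inside a stop range. This is a share of values, not of patients. Counts of 25 to <50 meet no trigger.

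Two worked patients:

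- Platelets 20 at entry and on Day 1. Since 10 < 20 < 25, the interrupt value is met with a change of 0. Since 20 equals baseline, the resumption condition is met at the same moment.
- Hemoglobin 7 at entry and on Day 1. Since 6 < 7 < 8, the interrupt value is met with a change of 0.

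Other entry limits that bear on such a patient: exclusion 6 (platelet disorder), exclusion 9 (recent gastrointestinal bleeding), exclusion 12 (unstable condition or laboratory abnormality), ECOG 0-1, life expectancy, and recovery from significant toxicity of prior therapy. None sets a count. Exclusion 6 rests expressly on investigator judgement, and criterion 8 itself admits autoimmune platelet destruction.

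After adding floors of 25 and 8: eligible platelets (at least 25) and the triggers (<25) share no value, and eligible hemoglobin (at least 8) and the triggers (<8) share no value. The overlap is zero.

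**The case against.** The best reply is that 5.8.2 already answers the question. Its lists concern toxicities. It treats a return to baseline as resolution, so a count that never left baseline is not a toxicity. The 25% reductions follow related Grade 3 and 4 events. Sections 8.1.1 and 8.3 do not count a known abnormality that has not worsened as an adverse event. This stands as the more natural reading, and a reader who inferred that the protocol orders such a patient off drug on Day 1 would be going too far. It does not close the matter. The triggers are bare numbers, the non-hematologic rules beside them show that a causal qualifier was available, and 8.1.1 and 8.3 also let an abnormal value become an adverse event when it leads to a delay or dose change.

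The harm should also not be overstated. The reported human DLTs are hypotension, hepatobiliary abnormalities and fatigue (5.7.2), plus anemia and neutropenia at 4.4 mg/kg (5.7.1), above the PTCL doses of 2.7 and 3.1 mg/kg. No thrombocytopenia DLT is reported. The Medical Monitor reviews each patient's safety data (8.10.2), and platelets falling below 10 stop treatment on either reading.

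A reader might infer that the gap lies in the absence from 5.8.2 of the 5.8.1 sentence under which adverse events considered for dose reduction "should not include the events assessed by the Investigator as exclusively related to underlying disease". That sentence governs dose reduction only. It exempts nobody from interruption or discontinuation, so importing it would not help.

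Finally, the looser PTCL entry looks deliberate, and floors narrow it. That is a real cost, but the exception survives for platelets of 25 to <50. The patients lost are those at counts where 5.8.2, taken at face value, holds the drug.

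**Conclusion.** The point holds as a mismatch between the entry and dosing rules. Criterion 8 permits entry at platelets below 25 or hemoglobin below 8, and 5.8.2 attaches interruption or discontinuation to those values without saying that they must represent worsening. Hemoglobin below 6 leads to discontinuation only if it persists despite transfusion or an ESA. ANC and exception patients with platelets of 25 to <50 are unaffected.

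The documents do not say how many PTCL patients enter at such counts. A reader might take the 50% above to mean half of the exception patients, or infer a bias in ORR; neither is supported. The absolute cut-offs still protect once a count falls into a lower band, so the ambiguity is confined to patients who start inside a stop range. The conclusion rests on the written text alone; operational guidance to sites, if any, was not available. It should be corrected at the next amendment, as a clarity and safety matter and not as a threat to the analysis.

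**What to change.** In criterion 8 of section 4.3 and in the synopsis, require platelets of at least 25 x10^9/L under the exception and hemoglobin of at least 8 g/dL, with transfusion permitted. Both values are the existing 5.8.2 interrupt cut-offs; the sponsor's clinicians should confirm them.

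Keep the 5.8.2 cut-offs absolute. Making them relative to baseline would need a definition of worsening that the protocol lacks. It could also weaken the stop at platelets below 10: a patient entering at 12 might fall below 10 without meeting a relative rule.

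The cost is amended wording in two places and no new procedure, since hematology is already measured in the week before dosing. A few severely cytopenic patients become ineligible. Patients entering just above 25 or 8 may still be held after a small fall, but that hold would then reflect a change on study.
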